## 4.9.3. Follow-up and Outcome Ascertainment Periods

The primary outcome will be obtained by exhaled carbon monoxide level at the final prenatal visit, within 4 weeks of delivery. If the patient has been lost to follow up prior to delivery, every attempt will be made to obtain an exhaled carbon monoxide level at admission for delivery. Patient satisfaction will also be assessed at the final measurement. Each patient will be asked about number of cigarettes smoked per day for the last week at each prenatal visit. Delivery outcomes will be assessed prior to discharge.

## 5. Statistical Considerations

## 5.1 Sample Size for Primary Outcome

In order to calculate our sample size, we targeted an alpha of 0.05 and a power of 90%. Based on our clinic population, we estimated the prevalence of smoking ≥10 cigarettes/day among women with substance use disorders who smoke at delivery is 90%. We target a reduction to 50% of women smoking ≥10 cigarettes/day at delivery in the intervention group. With a 20% loss to follow up, the required sample size is 74 women (37 women per group).

Baseline	Targeted	Relative Risk	Number per	Total Sample
Estimate of	Prevalence of		group	Size with
Smoking ≥10	Smoking ≥10			20% Loss to
cigarettes/day	cigarettes/day			Follow UP
at delivery	at delivery			
90%	60%	0.67	49	118
	50%	0.55	31	74
	40%	0.44	21	50
80%	60%	0.75	119	286
	50%	0.63	58	140
	40%	0.5	35	84

## 5.2. Power for Other Outcomes

We will have ample power to detect differences in the secondary outcomes of number of cigarettes smoked at final visit, average exhaled carbon monoxide, and average percent fetal carboxyhemoglobin between groups. Infant outcomes are likely to be underpowered and are considered exploratory. Similarly, patient satisfaction with the Smokerlyzer® device is an exploratory analysis.

## 6. Future studies

If this small trial demonstrates efficacy in smoking reduction in women with substance use disorders, we will pursue two future avenues of study. 1) Use of the expired maternal carbon monoxide and associated fetal carboxyhemoglobin to encourage smoking cessation in the general pregnancy population. 2) A larger study of women with substance use disorders to detect smaller improvements in smoking cessation and long-lasting smoking cessation post-partum.

## 8. Appendix

## **8.1 Smoking Cessation Resources**

## **Smoking During Pregnancy**

Smoking during pregnancy is unhealthy for you and your baby. Smoke from cigarettes, pipes, and cigars contains many chemicals that can cause cancer (*carcinogens*). Cigarettes also contain a stimulant drug (*nicotine*). When you smoke, harmful substances that you breathe in enter your bloodstream and can be passed on to your baby. This can affect your baby's development.

If you are planning to become pregnant or have recently become pregnant, talk with your health care provider about quitting smoking.

## How does smoking affect me?

Smoking increases your risk for many long-term (*chronic*) diseases. These diseases include cancer, lung diseases, and heart disease. Smoking during pregnancy increases your risk of:

- Losing the pregnancy (*miscarriage* or *stillbirth*).
- Giving birth too early (*premature birth*).
- Pregnancy outside of the uterus (*tubal pregnancy*).
- Having problems with the organ that provides the baby nourishment and oxygen (*placenta*), including:
  - Attachment of the placenta over the opening of the uterus (placenta previa).
  - Detachment of the placenta before the baby's birth (placental abruption).
- Having your water break before labor begins (premature rupture of membranes).

## How does smoking affect my baby?

## **Before Birth**

Smoking during pregnancy:

- Decreases blood flow and oxygen to your baby.
- Increases your baby's risk of birth defects, such as heart defects.

- Increases your baby's heart rate.
- Slows your baby's growth in the uterus (*intrauterine growth retardation*).

## **After Birth**

Babies born to women who smoked during pregnancy may:

- Have symptoms of nicotine withdrawal.
- Need to stay in the hospital for special care.
- May be too small at birth.
- Have a high risk of:
  - Serious health problems or lifelong disabilities.
  - Sudden infant death syndrome (SIDS).
  - Becoming obese.
  - Developing behavior or learning problems.

## What can happen if changes are not made?

When babies are born with a birth defect or illness, they often need to stay in the hospital longer before going home. Hospital stays may also be longer if you had any complications during labor or delivery. Longer hospital stays and more treatments result in higher costs for health care.

Many health issues among babies born to mothers who smoke can have a lifelong impact. This may include the long-term need for certain medicines, therapies, or other treatments.

## What are the benefits of not smoking during pregnancy?

You have a much better chance of having a healthy pregnancy and a healthy baby if you do not smoke while you are pregnant. Not smoking also means that you will have a better chance of living a long and healthy life, and your baby will have a better chance of growing into a healthy child and adult.

## What actions can be taken?

Quitting smoking can be difficult. Ask your health care provider for help to stop smoking. You may also consider:

- Counseling to help you quit smoking (*smoking cessation counseling*).
- Psychotherapy.
- Acupuncture.
- Hypnosis.
- Telephone QUIT hotlines.

If these methods do not help you, talk with your health care provider about other options. **Do not** take smoking cessation medicines or nicotine supplements unless your health care provider tells you to.

## Where to find more information:

Learn more about smoking during pregnancy and quitting smoking from:

- March of Dimes: www.marchofdimes.org/pregnancy/smoking-during-pregnancy.aspx
- U.S. Department of Health and Human Services: women.smokefree.gov
- American Cancer Society: www.cancer.org
- American Heart Association: www.heart.org
- National Cancer Institute: www.cancer.gov

## For help to quit smoking:

• National smoking cessation telephone hotline: [name]

## Contact a health care provider if:

- You are struggling to quit smoking.
- You are a smoker and you become pregnant or plan to become pregnant.
- You start smoking again after giving birth.

## **Summary**

- Tobacco smoke contains harmful substances that can affect a baby's health and development.
- Smoking increases the risk for serious problems, such as miscarriage, birth defects, or premature birth.
- If you need help to quit smoking, ask your health care provider.

This information is not intended to replace advice given to you by your health care provider. Make sure you discuss any questions you have with your health care provider.

Document Released: 05/01/2006 Document Revised: 10/06/2017 Document Reviewed: 10/06/2017 Elsevier Interactive Patient Education © 2018 Elsevier Inc.

# PREGNANT & SMOKING? ENROLL IN THE SIGS TRIAL

(Smoking Reduction In Gravid Substance-Users)

## Eligible:

- 16-years-old or greater
- Singleton pregnancy
- Less than 24 weeks gestation
- Interested in quitting smoking
- OBCC patients

#### Ineligible:

- Multi-fetal gestation
- >24 weeks gestation
- · Not interested in smoking cessation
- Fetal anomalies or genetic abnormalities
- · Fetal growth restriction

Questions? Page [name] @ [contact] or talk to your provider about the study

# **Smøkerlyzer®**

Breath carbon monoxide monitors Helping people to stop smoking

COppm-WCOHb calculation taken from: Jarvis M et al (1986) "low cost Carbon Monoxide monitors in smoking assessment."
 Thorax 41 pp 886-887.

COppm-NFCOHb calculation taken from: Gomez C. et al (2005)
 Expired air carbon monoxide concentration in mothers and their spouses above 5ppm is associated with decreased fetal growth." Preventive Medicine 40 pp 10-15

Ad	ult
COppm	%сонь ๋
30	5.43
29	5.27
28	5.11
27	4.95
26	4.79
25	4.63
24	4.47
23	4.31
22	4.15
21	3.99
20	3.83
19	3.67
18	3.51
17	3.35
16	3.19
15	3.03
14	2.87
13	2.71
12	2.55
11	2.39
10	2.23
09	2.07
08	1.91
07	1.75
06	1.59
05	1.43
04	1.27
03	1.11
02	0.95
01	0.79

Having a reading in this zone indicates you may well be a regular smoker with higher levels of CD in your blood. Do not despair! Help is at hand and your stop smoking visor can help you to give up smoking and lower your reading into the target "Green zone". light smoker or a non-smoker breathing in poor air quality or passive smoke. Your stop smoking advisor will be able to advise on the best course of action to lower this reading to the target "Green zone" This is where you really need to be! It means you have less than 25 carbon monoxide (CO) in your blood. Most people have a small amount of CO in their breath, this is due to the air quality around you.

СОррт %FCOHb 20+ 5.66 19 5.38 18 5.09 17 4.81 16 4.53 4.25 14 3.96 13 3.68 3.40 11 3.11 10 2.83 09 2.55 08 2.26 07 1.98 0.28

O Bedforf\* Scientific Limited 2018 Registered in England and Wales. Registered No:1289798 Our family, innovating health, for yours.

## 8.5 Patient Questionnaire

Smoking Reduction In Gravid Women with Substance Use Disorders (SIGS): A Randomized Controlled Trial

## Positive and Negative Affect Schedule (PANAS-SF)

Indicate the extent you have felt this way over the past week		Very slightly or not at all	A little	Moderately	Quite a bit	Extremely
PANAS 1	Interested			3	0 4	
PANAS 2	Distressed	 		 3	0 4	
PANAS 3	Excited	 		3	0 4	
PANAS 4	Upset	 		3	0 4	
PANAS 5	Strong			3	4	
PANAS 6	Guilty	 		 3	4	
PANAS 7	Scared			3	4	
PANAS 8	Hostile			3	4	
PANAS 9	Enthusiastic			3	4	
PANAS 10	Proud			3	4	
PANAS 11	Irritable	 		 3	4	
PANAS 12	Alert	 		3	4	
PANAS 13	Ashamed			3	4	
PANAS 14	Inspired			3	4	
PANAS 15	Nervous			3	4	
PANAS 16	Determined			3	4	
PANAS 17	Attentive			 3	4	

PANAS	Jittery	 		3	4	
18						
PANAS	Active		2	○ 3	4	 
19						
PANAS	Afraid		2	○ 3	4	 
20						

8.	6 Patient Survey									
	Smoking Reduction I	n Gr	avid Wom	nen wi	th Substar	ice Us	se Disord	ders (S	IGS):	
		ΑΙ			ntrolled Tr	ial				
				ent Sur	vey*					
_	lame:	MR					Study I			
	e final part of your participation in	n the	e research	study	is to comp	olete 1	this shor	t surve	ey. This sho	ould ta
a t	total of 15 minutes of your time.									
Ρle	ease circle the appropriate number	r for	each ques	stion:						
1.	Overall, how satisfied are you wit	th th	e support	you h	ave receiv	ed to	stop sm	oking?	)	
	Van Uncatisfied Una	satis	fied	lnaura		atisfi	ad	1/05	Catisfied	
	Very Unsatisfied Uns 1	satis 2	nea c	Jnsure 3	: 3	4	eu	very	Satisfied 5	
	1	۷		5		7			3	
2.	Would you recommend using the	e car	bon mond	oxide r	eading dev	vice (S	Smokerly	yzer) to	o other sm	okers
	who a want to stop smoking?									
								No	Unsure	Yes
								1	2	3
3.	In the event that you started sm	okin	ng again w	ould v	ou use the	Smo	kerlyzer	device	e to help w	ith
	stopping smoking?		.0 -0	,			,			
								No	Unsure	Yes
								1	2	3
4.	, , ,	t aga	iin and we	ere still	smoking,	would	d you pa	rticipa	te in the st	udy
	again?							No	Unsure	Yes
								1	2	3
5.	Have you smoked since your las	t pre	enatal app	ointm	ent?					
								No	Unsure	Yes
								1	2	3
6.	How satisfied are you with how	tha i	cupportiv	o ctoff	has boon?	)				
Ο.	Very UnsatisfiedUnsatisfied	tile :	Unsure	e Staii	Satisfied		Very S	atisfie	d	
	1	2	01.00.0	3		4	, .		5	
7.	•	n and	d advice th	nat sta	ff have giv	en to	you dur	ing yo	ur appointr	ment
	been?				C 1; (; 1		., .	ı. c.		
	Very UnsatisfiedUnsatisfied	2	Unsure	3	Satisfied	4	Very S	atisfie	a 5	
	1	2		3		4			3	
8.	How helpful has the written info	orma	tion that	staff h	ave given	to you	u been?			
	·				J	,		No	Unsure	Yes
								1	2	3
_						10				
9.	Do you find having your carbon	mon	ioxide (CC	)) read	ing helpfu	1?		No	Unsure	Yes
								1	2	3
								_	_	_

If there are any changes that you would like to see to the SIGS Trial, or if there was anything they did particularly well, then please write them here:

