## 3.2. Secondary Research Questions

- Does eCO monitoring decrease the number of cigarettes smoked per day?
- Does eCO monitoring increase infant birth weight?
- Does maternal eCO at delivery correlate with infant birth weight?
- Does maternal eCO prior to 24 weeks correlate with infant birth weight?
- Does percent fetal carboxyhemoglobin at final measurement correlate with birth weight?
- Does eCO monitoring at delivery correlate with APGAR scores?
- Does eCO monitoring increase gestational age at delivery?
- Does eCO monitoring improve patient satisfaction with prenatal care and smoking cessation?

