## 4.5. Management of control group

At each prenatal visit, in addition to receiving standard prenatal care, women randomized to the intervention group will:

- 1) Be asked to report how many cigarettes they have smoked per day in the last week
- 2) Measure eCO
- 3) Receive smoking cessation materials if reports continued smoking

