## 4.9.2. Secondary outcomes

- 1. Average number of cigarettes smoked/day in each group, as measured by exhaled carbon monoxide at final measurement
- 2. Prevalence of smoking ≥10 cigarettes/day in each group at delivery, per patient report
- 3. Average number of cigarettes smoked/day in each group, per patient report
- 4. Average exhaled carbon monoxide at final measurement
- 5. Average percent fetal carboxyhemoglobin at final measurement
- 6. Infant birthweight
- 7. APGAR at 5 minutes
- 8. Small for gestational age at birth (<10th percentile)
- 9. Gestational age at delivery

10. Patient satisfaction at final prenatal visit, measured by PANAS scales (positive and negative affect scales) and select questions on Stop Smoking Service Client Satisfaction Survey

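### Survey item 3 presupposes that the woman has stopped smoking, which the plan's own rates make untrue for most respondents, so its answers can partly reflect smoking status

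*Combined protocol and SAP*

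**What the plan says.** Section 8.6 (Patient Survey) tells each woman to "circle the appropriate number" for every question. Item 3 opens "In the event that you started sm" (the extracted text breaks off mid-word) and asks whether, if she took up smoking again, she would use the Smokerlyzer to help her stop. The answers are No, Unsure and Yes, with no choice for a woman who is still smoking. Item 4 mentions women still smoking and item 5 asks about smoking since the last prenatal appointment, but neither routes anyone past item 3.

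Item 8 opens "How helpful has the written info" and concerns the written material from staff. It too offers only No, Unsure and Yes.

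The survey feeds secondary outcome 10 in Section 4.9.2, which combines the PANAS with "select questions on Stop Smoking Service Client Satisfaction Survey". Section 3.2 poses the question between arms: "Does eCO monitoring improve patient satisfaction with prenatal care and smoking cessation". Section 5.2 says that "patient satisfaction with the Smokerlyzer® device is an exploratory analysis". The plan does not list which survey questions count, how they are scored or how they are tested.

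Under Section 3.4 every woman enters smoking at least 10 cigarettes a day. Section 5.1 puts the share still doing so at delivery at 90% without the intervention and states: "We target a reduction to 50% of women smoking ≥10 cigarettes/day at delivery in the intervention group". On leaflets, Section 4.5 has control women "Receive smoking cessation materials if reports continued smoking". Section 4.4 adds a positive eCO reading as a second trigger in the intervention arm, and Section 3.3 reads as supply at every visit in that arm.

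**The concern.** A woman who has never stopped cannot start again, yet she is asked to circle an answer. If she circles No or Unsure because the question does not describe her, the answer says something about her smoking and little about her view of the device. Stopping is what the intervention is meant to change, so the share of women in this position may differ by arm. A difference on item 3 could then appear with equal willingness to use the device in both arms. The regression adjustment foreseen in Section 5.3 would not remove it if it uses baseline covariates, because stopping happens after randomisation.

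At stake is the reading of one item within the satisfaction outcome. Item 8 raises a smaller point: its question asks for a degree and its scale gives a yes/no answer, so a No could mean either not helpful or none received.

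**Working it through.** **The plan's own figure.** Section 5.1 gives 31 per group for 90% versus 50%, alpha 0.05 (two-sided assumed) and power 90%. The two-proportion formula gives 26 per group without a continuity correction and 31 with it, so the figure reproduces. The total of 74 is 2 × 31 × 1.2 = 74.4. I therefore take 31 per group as the evaluable number and 37 as the number randomised.

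**Women whom item 3's premise does not fit.** The survey is completed around delivery (Sections 4.7 and 4.9.3), the time to which Section 5.1's rates apply.

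| | Control (90%) | Intervention (50%) |
|---|---|---|
| Still at ≥10/day, of 31 | 0.90 × 31 = 27.9 | 0.50 × 31 = 15.5 |
| Still at ≥10/day, of 37 | 0.90 × 37 = 33.3 | 0.50 × 37 = 18.5 |
| Could have stopped, at most, of 31 | 0.10 × 31 = 3.1 | 0.50 × 31 = 15.5 |

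At 1:1 allocation this is (0.90 + 0.50)/2 = 70% of respondents. The first two rows are minimums for women who have not stopped, because those smoking 1-9 a day have not stopped either.

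**Possible spurious arm difference on item 3.** Let g be the intervention-minus-control difference in the proportion who have stopped. Let d be the difference in Yes rate between women who have stopped and women who have not, caused by the wording alone. With equal true willingness in both arms, the arm difference is g × d. The documents give neither g nor d, so all the values below are assumptions.

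| Gap in stopping, g | d = 20 points | d = 40 points | d = 60 points |
|---|---|---|---|
| 0 | 0 | 0 | 0 |
| 10 points | 2 | 4 | 6 |
| 40 points | 8 | 16 | 24 |

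The 40-point row borrows the planned gap in heavy smoking (90% − 50%). It counts every woman below 10 a day in either arm as having quit, so it is an extreme case and not an estimate. The direction is also assumed: the difference favours the intervention only if more intervention women stop and stopped women say Yes more often.

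**Item 8.** No figure can be derived. The mismatch between question and scale is the same in both arms. All women enter at ≥10 a day and qualify for material at any visit where they report smoking. The item is not limited to the last visit, so one receipt is enough, and women who received nothing should be rare in either arm.

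**The case against.** The best defence is that item 3 is hypothetical and a current smoker can guess what is meant. A woman who stopped and relapsed can also make sense of it, and the documents do not count such women. Items 4 and 5, with the self-report and eCO taken at every visit, let an analyst read item 3 by smoking status. Satisfaction is exploratory and no item-level comparison is specified.

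Much of this stands. It rules out several stronger conclusions that a reader might draw:

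- *That the items cannot be answered.* Both can. Item 3 rests on a premise that does not fit most respondents, and item 8 can be read as a plain question of whether the material helped.
- *That the arms differ by construction.* They differ only if the intervention makes more women stop. The 90% and 50% are a planning estimate and a target; with equal stopping the bias is zero.
- *That the bias is 40 points times some fraction.* This treats smoking fewer than 10 a day as stopping, and the documents give no quit rate.
- *That item 8 compares receipt of leaflets.* The supply rules do differ by arm, but almost every woman should receive material at least once.

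The defence does not remove the point about item 3. Items 4 and 5 neither route women past it nor repair its premise. Reading it by smoking status afterwards helps description, but groups formed on a post-randomisation result are no longer a randomised comparison.

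**Conclusion.** The point holds as a wording fault in item 3, of minor weight. On Section 5.1's rates the premise does not fit at least about 28 of 31 evaluable controls and 15-16 of 31 intervention women. The answers can therefore carry smoking status, and unequally by arm if the intervention works. The size is unknown: from 0 to 24 percentage points across the cases shown, with the upper end resting on an extreme gap in stopping and an assumed effect of the wording. Item 8 has a small mismatch of question and scale that does not favour either arm, and it lacks a choice for women who received nothing.

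A reader might infer that the trial's main conclusion is affected. It is not: the primary outcome is measured by eCO and does not use the survey. The effect is confined to the exploratory satisfaction outcome.

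**What to change.** In Section 8.6:

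- Reword item 3 so that it applies to quitters and current smokers alike, for example: *If you wanted to stop smoking in the future, would you use the Smokerlyzer device to help?*
- Match item 8's question to its existing scale, for example: *Was the written information staff gave you helpful?* Add the choice *Did not receive any*. Moving the item to the five-point satisfaction scale is not needed and would change what it measures.

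If forms with the present wording have already been collected, report item 3 descriptively by smoking status, using item 5 and eCO, and draw no conclusion about the arms from it. Use the two together, since by Section 2.4 carbon monoxide persists for at most about 24 hours.

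The cost is two edited items, one added answer choice and an IRB wording amendment. Old and new forms would not be directly comparable on these two items.
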